**Background, Rationale and Context**

There is evidence that the current design and content provided by most biomedical research informed consent documents do not consistently meet the expectations researchers place on them to effectively inform research participants of information thought to be most important in facilitating their ability to make informed decisions about participation (Denzen et al., 2012). The need for revisions to the informed consent document design is supported by empirical research. Joffe et al. found in their 2001 study of 200 people in the United States participating in cancer trials that 70% of those interviewed did not realize that the treatments they were undergoing had not yet been proven effective, and 63% did not understand that additional risks were posed by participating in the research. In a manuscript published in 2008, Bergenmar, Molin, Wilking, and Brandberg reported that over half of the 325 patients consenting to phase I and II cancer trials incorrectly responded to questions about the unapproved nature of the study treatment and risks of participation.

The importance of informed consent in ensuring that participants in clinical research are provided the opportunity to make autonomous choices is a paramount ethical premise in human research. The effectiveness of consent document design and consent process to accurately and fully convey the elements of informed consent is critical and deserves further study. Development of an improved informed consent document design for clinical studies would be a valuable contribution to human research. With this study we seek to collect pilot data on a novel consent form design that incorporates a modified version of the “chunking” theory of learning. Clifton A. Casteel (1990) found that chunking sentences or phrases in text into related groupings resulted in a positive significant improvement in reading comprehension among students with poor reading skills. Because the information contained in consent documents in large epidemiologic studies is complex, detailed, and novel for potential research participants, the use of a modified form of chunking (grouping the related sections of consent into smaller documents), may be an effective and low cost way of improving comprehension of the elements of consent.

## **Objectives**

This pilot study will examine the effectiveness of the New Executive and Appendix Template (NEAT) form when used in the consent process for individuals participating in the Atherosclerosis Risk in Communities (ARIC) Neurocognitive Study. Specifically, the primary objective of the study is to:

1. Determine if participants who receive the NEAT form report greater comprehension (as measured by the total score on the Comprehension tool instrument) at the end of the consent process, than participants who receive a standard form.

The secondary objectives are to:

1. Determine what types of characteristics participants value in a consent form, via a qualitative analysis of responses to the question “What do you like best, if anything about this consent form? and What do you like least, if anything about this consent form?”
2. Determine what types of characteristics study team members find helpful or burdensome when utilizing a consent form during the consent process.

Participation in the NEAT study will involve randomization of study participants to either the traditional consent form (detailing the ARIC study) or the NEAT form and the materials that accompany it (also detailing the ARIC study). The consent process will be conducted in the usual manner using the document to which the participant was randomized (NEAT or Traditional). Following the consent process, the interviewer will administer the Comprehension tool, a questionnaire which will measure participants' comprehension (Part 1) and opinions about the layout of the tool (Part 2). A qualitative analysis of the open-ended questions (Part 2) will provide subjective data on participant's opinions of the form design and arrangement, or other factors that they consider important. The Comprehension tool score and the qualitative data about the consent form qualities make up the outcomes to be measured. Ultimately, these data will provide pilot data showing whether differences in comprehension or subject preference may exist between the two consent form designs.

## **Methods and Measures**

### **Design**

This study will be conducted in conjunction with the consent process for the ARIC study in the Division of Public Health Sciences. The IRB approved consent forms will be presented to ARIC participants by the same study staff that would usually conduct the research consent process. The consent form will be either

the regular IRB approved version, or the same form presented in components placed within a bi-fold folder. The consent form wording will be unchanged between the two versions.

The NEAT form consists of a clear and concise overview document containing information satisfying all elements of consent. This is made up of IRB-approved wording from the regular consent form. More detailed information, such as specific clinic measures are provided as additional material and are discussed during the consent process after the general overview has been provided with the NEAT form. The HIPAA Authorization is provided as a separate document.

Approximately 200 participants will be randomized (via birth month) to receive either the regular form or the NEAT form. Following the consent process, each participant will be interviewed using the Comprehension tool measure. This design provides an opportunity to test a new consent form design in a real-world environment with all of the accompanying uncertainty that affects comprehension during the clinical research consent process.

If a participant scores poorly on the comprehension tool, elements of consent will be revisited in order to ensure appropriate understanding of the study information. A copy of the Comprehension tool is included as an appendix to this protocol.

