### **Setting**

This study will take place at a place consistent with the plan approved by the IRB for the ARIC study . Potential subjects will be identified by ARIC study staff in accordance with the ARIC protocol.

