### **Subjects selection criteria**

- **Inclusion Criteria**

Individuals who are eligible for the ARIC study, with which this pilot study is cooperating.

- **Exclusion Criteria**

Any individuals not eligible for the ARIC study.

- **Sample Size**

The proposed study is intended to be a pilot study to examine the impact of a novel consent form methodology on participant comprehension. The proposed enrollment is 100 participants in each arm of the study for a total of 200.

**All study team members** will be trained to administer the NEAT form and the comprehension tool.

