### **Analytical Plan**

Study participants will be randomized 1:1 to either the traditional versus NEAT consent documents. Differences in comprehension will be assessed by the Comprehension tool, which is an instrument to assess research consent comprehension.

Summary scores from the Comprehension tool will be analyzed initially using descriptive statistics which will be helpful in planning of a larger trial in the future. To test the differences in comprehension between the two consent forms, we will use a t-test (assuming the assumptions of the test are met) and compare the summary scores. The qualitative feedback will be reviewed to see if any consistent themes are present, both overall and by group.

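### Allocation by birth month is foreseeable and not random, yet the plan calls it randomised and describes no sequence, concealment or allocation record

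*Combined protocol and SAP*

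**What the plan says.** The method appears once, in the Design section: "Approximately 200 participants will be randomized (via birth month) to receive either the regular form or the NEAT form". The Objectives also describe participants as randomised to a form, and the Analytical Plan adds the ratio: "Study participants will be randomized 1:1 to either the traditional versus NEAT consent documents". The sample-size paragraph under Subjects selection criteria reads "The proposed enrollment is 100 participants in each arm of the study for a total of 200".

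On who does what, the Setting section says "Potential subjects will be identified by ARIC study staff in accordance with the ARIC protocol", and the Design section says the forms are "presented to ARIC participants by the same study staff that would usually conduct the research consent process". Subject Recruitment Methods adds that participants already belong to the ongoing ARIC study.

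For the primary objective, whether NEAT recipients comprehend more, the Analytical Plan says "we will use a t-test (assuming the assumptions of the test are met) and compare the summary scores". It describes no adjustment. It also says summary scores will be "analyzed initially using descriptive statistics which will be helpful in planning of a larger trial in the future".

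**The concern.** Randomisation needs a chance step that sets the arm after, and independently of, the decision to approach a person. Birth month provides none. Choosing the month-to-form mapping at random would not help, because the arm stays predictable once the mapping is known.

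The possible harm is selective approach. Staff who can foresee the form may, knowingly or not, approach some people less readily, or at another time, when a particular form would follow. A difference in comprehension scores would then partly reflect who was approached. The t-test cannot separate the two, and any by-arm means carried into planning the larger trial would hold the same bias.

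The concern is not that birth month itself affects comprehension. It is that the rule is foreseeable and that the label claims a protection the method does not give.

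**Working it through.** **1. The text set side by side.** Design gives birth month as the mechanism. Objectives, Design and Analytical Plan all use the language of randomisation. The available text does not say which months go to which form. It describes no generated sequence, no concealment step and no record of each allocation. The Analytical Plan reviews feedback by group, so the arm must be captured somewhere, but how is not described.

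**2. Can staff foresee the arm?** ARIC staff identify people who are already in ARIC, and the usual staff present the form. That they know birth months is a reasonable inference; no section states it.

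**3. The plan's own figure.** 100 + 100 = 200, as stated. The size cannot be derived further, because no significance level, power, effect size or SD is given.

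**4. Birth month does not secure the planned split.** Assume half of participants fall in each set of months. With X ~ Binomial(200, 0.5):
- P(X = 100) = 5.6%.
- P(one arm has 90 or fewer) = 17.9%.

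**5. Illustration of selective approach.** From the plan: 100 per arm. Assumed: two-sided 5% test, no true effect, and one-way omission from the NEAT arm with replacement by people like those retained. Let *f* be the share of the NEAT arm omitted, and *g* their shortfall in SD from the mean of the unselected arm.

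Setting the unselected mean to 0, f × (−g) + (1 − f) × m = 0, so the retained mean, which is the bias, is m = f × g / (1 − f). For f = 0.10 and g = 0.5: 0.10 × 0.5 / 0.90 = 0.056 SD.

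The false-positive rate comes from the noncentral t distribution with 198 df and noncentrality m / √(2/100).

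| Omitted | g = 0.25 SD | g = 0.5 SD | g = 1 SD |
|---|---|---|---|
| 5% | 5.1% | 5.4% | 6.6% |
| 10% | 5.4% | 6.8% | 12.2% |
| 15% | 6.1% | 9.5% | 23.7% |

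The biases in the 10% row are 0.028, 0.056 and 0.111 SD. Simulation of that row (20,000 runs) gave 5.5%, 6.9% and 12.4%. For the 15%, 1 SD cell it gave 25.2%, slightly higher because omission also shrinks the NEAT-arm variance.

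**6. What it takes to double the error rate.** A 10% rate needs a bias of 0.0927 SD. Solving f = 0.0927 / (g + 0.0927) gives 27%, 16% or 8.5% of the arm omitted at gaps of 0.25, 0.5 or 1 SD.

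**7. Scale.** 100 per arm detects 0.398 SD with 80% power. With 10% omitted, the bias is 0.028/0.398 = 7%, 0.056/0.398 = 14% or 0.111/0.398 = 28% of that.

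**The case against.** The strongest reply is that the route to bias may be narrow. Staff identify people under the ARIC protocol, eligibility is simply ARIC eligibility, and consent follows the usual process, all of which leaves little room for discretion. This stands in part. The ARIC protocol is not in these documents, and nothing available says that every eligible person is approached, so the risk is neither shown nor excluded.

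The numbers are also modest. Seven of the nine cells stay below 10%, and the top of the range comes from one corner. If the gap is measured against those retained, the bias is f × g, and the two largest cells fall from 12.2% to 10.8% and from 23.7% to 18.4%. This stands: the table is an illustration on assumed inputs, not an estimate.

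Third, this is a pilot, and it discloses the method openly. That lowers the stakes. It does not remove the point, because the primary objective is comparative and a between-form test is planned.

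Finally, the front pages were removed and the Comprehension tool is named in the Appendix but not shown, so an arm field on that form cannot be ruled out. The statement about the missing allocation record therefore covers only the available text. The main point does not depend on it.

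**Conclusion.** The concern holds and should be fixed. That allocation is quasi-random, foreseeable and mislabelled follows directly from the Design section, and no other section repairs it. This part is certain.

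The consequence is less certain. It requires staff to know the rule and the birth months, and to have some discretion over whom or when they approach; neither is stated. Over 5% to 15% omitted and gaps of 0.25 to 1 SD, the false-positive rate runs from 5.1% to 23.7%, and it stays close to nominal unless selection is strong. Whether selective approach could be detected afterwards is unclear. Subject Recruitment Methods says no identifiers are recorded, Confidentiality and Privacy refers to subject identifiers not linked to identifiable information, and the data form is not shown.

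**What to change.** **Preferred change**
- *Design:* replace the birth-month rule with a computer-generated 1:1 list in permuted blocks of varying size, revealed only once the person has been identified and the consent session begins. Sequentially numbered, opaque, sealed envelopes, each holding a card naming the form, would deliver it. Another concealed route would serve. REDCap is an option only if it is available at the point of consent; the plan mentions it only for later data entry.
- *Record:* put a non-identifying allocation number on the Comprehension tool, and keep an anonymous log of each allocation and the form used. Say so in Confidentiality and Privacy, and make its wording on identifiers agree with Subject Recruitment Methods.
- *Analytical Plan:* state that the primary comparison analyses participants by assigned form. This is a separate safeguard against swapped forms, which concealment does not prevent.

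**If birth month must be kept**
- Call the design quasi-randomised in Objectives, Design and Analytical Plan.
- State the month-to-form rule in advance.
- Approach people consecutively, and report anonymous counts approached and declined by arm.
- Limit the causal conclusion.

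This fallback makes selection visible but leaves the arm foreseeable.

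**Cost of the preferred change.** One random list, about 200 envelopes, a one-page log, edits to four sections and an IRB amendment. Both forms must be at hand at each session. No extra participants are needed, anonymity is kept, and blocking supports the planned 100 per arm.

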### **Human Subjects Protection**

### **Subject Recruitment Methods**

Describe how and where subjects will be identified and recruited. Indicate who will do the recruiting, and tell how subjects will be contacted. Describe efforts to ensure equal access to participation among women and minorities. Describe how you will protect the privacy of potential subjects during recruitment.

- Under this limited waiver, you are allowed to access and use only the minimum amount of PHI necessary to review eligibility criteria and contact potential subjects. What information are you planning to collect for this purpose?
  - Participants in this study are members of the ongoing ARIC study.
- How will confidentiality/privacy be protected prior to ascertaining desire to participate?
  - Participants in this study are members of the ongoing ARIC study.
- When and how will you destroy the contact information if an individual declines participation?
  - The IRB approved processes for the destruction of contact information will be utilized as usual with no necessary changes required by the NEAT study. The NEAT study will not involve the recording of any subject identifiers at any time.

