### **Confidentiality and Privacy**

Confidentiality will be protected by collecting only information needed to assess study outcomes, minimizing to the fullest extent possible the collection of any information that could directly identify subjects, and maintaining all study information in a secure manner. To help ensure subject privacy and confidentiality, no identifying information will be collected with the Comprehension tool form or likes/dislikes feedback. Subject identifiers will not be linked to any personally identifiable information. The comprehension tool will be conducted on paper directly after the consent process. After the tools are collected, they will be scored by the PI and then entered into REDCap for analysis. Data access to the data collection forms and the transcribed information in the electronic system will be limited to study team members. Data and records will be kept on the WF School of Medicine

campus in a locked office, and computer data will be password protected and secured on the WFBH network. No reference to any individual participant will appear in reports, presentations, or publications that may arise from the study.

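### Does scoring by the PI after collection, on forms without identifiers, defeat the promise to revisit consent after a poor score?

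*Combined protocol and SAP*

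**What the plan says.** Four parts of the protocol bear on the point.

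- **Design** makes the commitment: "If a participant scores poorly on the comprehension tool, elements of consent will be revisited in order to ensure appropriate understanding". It gives no cut-off and names nobody to act.
- **Objectives** describes the setting: "Following the consent process, the interviewer will administer the Comprehension tool". Confidentiality and Privacy adds the timing: "The comprehension tool will be conducted on paper directly after the consent process". Subjects selection criteria says that every study team member is trained to give the tool.
- **Confidentiality and Privacy** describes the handling of the completed forms: "After the tools are collected, they will be scored by the PI and then entered into REDCap for analysis". It also says that "no identifying information will be collected with the Comprehension tool form or likes/dislikes feedback".
- **Subject Recruitment Methods** goes further: "The NEAT study will not involve the recording of any subject identifiers at any time".

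The Analytical Plan compares summary scores between arms with a t-test and also calls for "descriptive statistics which will be helpful in planning of a larger trial in the future". The comprehension tool is an appendix to the protocol. Only its title appears in the text supplied.

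**The concern.** The trigger for re-explaining consent is a score. The only scoring that the text describes happens later, at the PI's desk, on sheets that cannot be traced to anyone. If that were the first look at the answers, the promise in the Design section could not be kept. A participant who had misunderstood the parent ARIC study would go uncorrected. That would be serious in a trial whose rationale is that misunderstanding is common.

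A second worry concerns the analysis. No sentence says that recorded answers stay as first given when consent is revisited. If interviewers corrected low-scoring sheets during a revisit, the spread of scores would shrink. The difference between arms could shrink too, and both figures are meant to inform a larger trial.

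**Working it through.** **1. Can the promise be kept as written?**

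| Question | Where answered | Answer |
|---|---|---|
| Who is with the participant when the tool is given? | Objectives; Subjects selection criteria | An interviewer trained to give the tool |
| When? | Confidentiality and Privacy | As soon as consent is finished |
| Is an identifier needed to re-explain then? | Follows from the two rows above | No, the participant is still present |
| What is the PI's scoring for? | Confidentiality and Privacy | Producing the score entered for analysis |
| Does any text make the PI's score the trigger? | None found | No |
| Does any text bar the interviewer from judging answers? | None found | No |

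The sentence on PI scoring belongs to an account of how data are stored and protected. It does not say that nobody looks at the answers earlier. A further sentence there, "Subject identifiers will not be linked to any personally identifiable information", gives no route back to a participant, but an immediate revisit needs none. The anonymity statements and the revisit commitment are therefore compatible.

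Two details remain open: who checks, and what counts as poor. The number of people who rely on them depends on an assumed rate of poor scores: 0.10 × 200 = 20, and 0.20 × 200 = 40.

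**2. Which score is analysed?**

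One administration is described, and its score is what prompts a revisit. The analysed score is then naturally the one obtained before the revisit. Nothing in the text mentions repeating the tool or altering answers.

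**3. What if answers were altered anyway?**

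The protocol gives no SD, effect size, alpha or power, so there is no figure of its own to reproduce. All inputs except 100 per arm are assumptions: normal scores with SD 1, a true difference of 0.40, and a two-sided 5% t-test. The lowest fraction p of an arm is raised by k = 1 SD.

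- Shift in arm mean = p·k.
- Arm variance = 1 + k²p(1 − p) − 2kφ(z_p), where z_p is the normal quantile at p and φ the normal density.

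With no alteration, power is 0.804, and 80% power needs 100 per arm.

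*20% altered in the traditional arm, 10% in the NEAT arm.*
- Difference: 0.40 − 0.20 + 0.10 = 0.30.
- Variances: 1 + 0.16 − 2(0.280) = 0.600 and 1 + 0.09 − 2(0.1755) = 0.739. Their mean is 0.670, so the SD is 0.818.
- Standardised difference: 0.30/0.818 = 0.367. Power is 0.732.

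*15% against 10%.*
- Difference: 0.40 − 0.15 + 0.10 = 0.35.
- Variances: 1 + 0.1275 − 2(0.233) = 0.661 and 0.739. Their mean is 0.700, so the SD is 0.837.
- Standardised difference: 0.35/0.837 = 0.418. Power is 0.837.

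Power therefore moves either way around 80%.

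For planning a later trial at 80% power, the result depends on which pilot figures are carried forward. True power is for unaltered scores with a difference of 0.40 and SD 1.

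| Figures used | Per arm | True power |
|---|---|---|
| Difference 0.40 kept, altered SD 0.818 | 67 | 63% |
| Altered difference 0.30 and altered SD 0.818 | 118 | 86% |
| Altered difference 0.35 and altered SD 0.837 | 91 | 76% |

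The first row pairs an unaltered difference with an altered SD. Taking both figures from the same pilot can make the later trial too large or too small. There is no consistent direction of harm, and every row needs a practice that the protocol does not describe.

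**The case for a change.** The best case for a change is ethical. The promise is firm and concerns valid consent to the parent study. The protocol's own background section argues that poor understanding is frequent. Training is described as covering administration of the tool, with no mention of scoring it or acting on it. Without a stated rule, each interviewer decides what is poor, and may be judging a consent discussion that he or she has just led. Closing the gap would cost two or three sentences and about a minute per interview, or 200 × 1/60 = 3.3 hours in all.

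Part of this stands. The text supplied names no checker and no threshold, and interviewers may differ. But this is a missing operating detail, and the promise remains workable without it. The staff are the usual ARIC consent staff, the participant is in front of them, and re-explaining any item answered wrongly would honour the commitment without a numerical cut-off. The appended form is the natural place for a key or an instruction, and its absence from the text supplied cannot be held against the plan. The low cost of an added sentence makes it a reasonable courtesy. It does not show that the plan is wrong.

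**Conclusion.** No change to the plan is called for. The revisit can take place on the spot without identifiers, and the PI's later scoring serves the analysis. The open points are a role and a threshold that trained interviewers would settle sensibly or that the appendix may settle. The number of participants concerned, 20 to 40 of 200, rests on an assumed 10% to 20% rate of poor scores.

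The primary comparison is sound as written. Concern about altered scores depends on a practice that is nowhere described. Even when that practice is assumed, power in the two cases worked runs from 73% to 84% against 80%, and the effect on a later trial's size has no fixed sign. The conclusion rests on reading the analysed score as the one that precedes any revisit, which is what the described sequence implies.
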